# 5. Statistical Analysis Plan

Main aim: The primary objective is to investigate the acute effects of a single dose of 300mg lemon balm on calmness and mood during cognitive overload in adults with subjective stress complaints.

Baseline characteristics will be homogenous across the two groups, placebo and intervention, respectively, as identified by pre-screening and screening criteria. The determined criteria include PSS scores between 14 to 26 to indicate stress problems, physical and emotional health, gender, age and lifestyle factors such as intake of daily fruit and vegetables (no more than 3 portions), no excessive caffeine or alcohol consumption, no excessive exercise, adequate performance on the cognitive tasks, and not on any restrictive diet (i.e., vegan/vegetarian) or medication.

# Primary Outcome Variable

To determine the effect of 300 mg lemon balm on ratings of calmness following a period of cognitive demand, measured using a 9-point Likert Scale, at baseline (0h) and 5 hours post administration. This Calmness 9-point Likert scale is scored from 1, "Not at all Calm" to 9, "Extremely Calm" Calmness Anchor points.

# **Exploratory Outcome Variables**

- To determine the effects of 300mg lemon balm on various mood measures (domains including fatigue and relaxation) measured at baseline (0h), 1h, 3h and 5h post administration.
- To determine the effects of 300mg lemon balm on cognition (specifically, executive function and memory) measured at baseline (0h), 1h, 3h and 5h post administration.
- Heart rate and aortic blood pressure will be taken in triplicate where averaged scores will be assessed at pre-(before 0h block) and post-test (after 5h block) to estimate tolerance to intervention versus placebo.

### **Analysis**

Before analysis, all data will be checked for assumptions of parametric testing, including Normal distribution, then assessed with boxplots to screen for any outliers. On recommendation of a statistician, all repeated measures data will be analysed using Linear Mixed Modelling (LMM) in RStudio v4.0. This technique can be used to model variance relating to both fixed parameters such as experimental doses and random parameters such as individual differences between subjects, within multiple layers of the same model. Models will be adjusted for potential predictive factors, such as sex, diet quality, physical activity level and severity of baseline stress complaints and/or baseline performance on cognitive tasks where the inclusion of these covariates improves the fit of the model, as long as assumptions are met. Subjects will be included as a random factor as a way of controlling for non-independence of data from the same subjects. The models will be applied in a systematic way to retain consistency between analyses. Where possible, an unstructured covariance matrix will be specified for the repeated observations on a subject within the same period. As LMMs do not require balanced data, subjects with missing data points will not be excluded from the analyses. Post-hoc Bonferroni-corrected parametric tests such as independent t-tests will be performed to estimate between-group differences between placebo and intervention groups, or within-group differences between time points, where appropriate.

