## 1. Sample Size Calculation

An a priori power analysis in G\* power with an effect size of 0.5 (Kennedy et al., 2003; Kennedy et al., 2004) indicated that a sample of 130 participants (65 per group, placebo and treatment respectively) with a 10% attrition rate would be necessary to achieve a power level of 0.80 at a significance level of 0.05. Similar trials investigating mood and cognition have shown a change from baseline following an acute dose of lemon balm beginning with changes first observed after 1h and maintained throughout the test day, in samples as small as 18 participants (Kennedy et al., 2004).

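### The primary calmness comparison is not prespecified as adjusted for 0h calmness, so precision available from data already collected is not secured

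*Combined protocol and SAP*

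**What the plan says.** - **Outcome.** Under Primary Outcome Variable, calmness is "measured using a 9-point Likert Scale, at baseline (0h) and 5 hours post administration". The section does not say whether the effect is the 5h difference, the difference in change, or a baseline-adjusted difference.
- **Model and covariates.** The Analysis section puts all repeated measures data into a linear mixed model with subject as a random factor and, where possible, an unstructured covariance matrix. On covariates it says "Models will be adjusted for potential predictive factors, such as sex, diet quality, physical activity level", and continues with "severity of baseline stress complaints and/or baseline performance on cognitive tasks where the inclusion of these covariates improves the fit of the model". Calmness at 0h is not named. Stress severity and baseline cognitive performance are different variables.
- **Between-arm comparison.** The only explicit one is a set of Bonferroni-corrected post-hoc tests, with the independent t-test as the example and no mention of baseline.
- **Sample size.** Section 1 reports "An a priori power analysis in G\* power with an effect size of 0.5", giving "a sample of 130 participants (65 per group, placebo and treatment respectively"), and says this number "with a 10% attrition rate would be necessary to achieve a power level of 0.80". It does not say which SD the effect size is scaled on. It describes similar earlier trials as ones that "have shown a change from baseline following an acute dose of lemon balm".
- **Baseline.** Section 5 says baseline characteristics "will be homogenous across the two groups, placebo and intervention, respectively, as identified by pre-screening and screening criteria".

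**The concern.** A mixed model does not adjust for baseline merely because the baseline value is in the data. If 0h and 5h calmness are both responses and each arm has its own 0h mean, the group-by-time term is a difference in change and the 5h group difference is a raw contrast. Neither a random subject effect nor an unstructured covariance alters that. The baseline-adjusted estimate needs either 0h calmness as a covariate or a single 0h mean shared by the arms. The plan states neither.

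Two things are at stake. The primary comparison may lose power that an existing measurement would supply. And because no term is named and covariates enter by fit, the choice among raw, change and adjusted contrasts stays open until the data are seen.

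The statement about homogeneous baselines gives no reason to skip adjustment. Eligibility limits such as a PSS of 14 to 26 narrow who enters; they do not equalise the randomised arms. In any case the gain comes from the 0h–5h correlation, not from correcting imbalance.

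**Working it through.** **Inputs.** From section 1: effect size 0.5 (read as a standardised mean difference d), 65 per arm, 10% attrition, power 0.80, alpha 0.05. Assumed: two-sided test; r from 0.3 to 0.7; equal SDs at 0h and 5h unless stated.

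**The plan's own figure.** For d = 0.5, a two-sided t-test needs 64 per arm (128) for 80% power, and 65 per arm gives 81%. So 130 matches the calculation without attrition. Allowing for 10% loss, 128/0.9 = 142.2, which is 143 in total (144 if rounded up per arm). If 130 already includes attrition, 130 × 0.9 = 117 are evaluable (58 and 59).

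**SD of each contrast**, in units of the 5h SD, with k = SD(0h)/SD(5h):
- raw 5h difference: 1
- difference in change: √(k² + 1 − 2rk), which is √(2(1 − r)) at k = 1
- adjusted for 0h: √(1 − r²), with one fewer degree of freedom

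At k = 1 the adjusted variance is (1 − r²) of raw and (1 + r)/2 of change. For example, at r = 0.5 the adjusted SD is √0.75 = 0.866, so the effective d is 0.5/0.866 = 0.577, against 0.5 for both simple contrasts.

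**Power (noncentral t, k = 1, d on a single rating), raw / change / adjusted:**

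| r | 117 evaluable | 65 evaluable per arm | n per arm for 80% |
|---|---|---|---|
| 0.3 | 76 / 62 / 80% | 81 / 67 / 84% | 64 / 89 / 59 |
| 0.5 | 76 / 76 / 87% | 81 / 81 / 90% | 64 / 64 / 49 |
| 0.7 | 76 / 93 / 96% | 81 / 95 / 98% | 64 / 39 / 34 |

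**Lower r (117 evaluable).** Adjustment adds about 0.4 points over raw at r = 0.1 and 1.7 at r = 0.2. At r = 0 the two are equal, so the lost degree of freedom is negligible. The change contrast falls to 52% at r = 0.1.

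**If d = 0.5 is on the SD of change**, the mean difference is 0.5√(2(1 − r)). Power with 117 evaluable is 89/76/91%, 76/76/87% and 55/76/83% at r = 0.3, 0.5 and 0.7.

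**If the SDs differ** (d on the 5h rating), change-contrast power at r = 0.3, 0.5 and 0.7 is 70/83/96% for k = 0.8 and 51/65/84% for k = 1.25. Adjusted power stays at 80/87/96%. Change is less precise than raw whenever r < k/2, that is below 0.40, 0.50 and 0.625 for k = 0.8, 1 and 1.25.

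**Simulation on rounded 1–9 scores** (SD 1.6, 58/59, 20,000 runs per r). Rejection rates at d = 0.5 were 0.75/0.60/0.79, 0.75/0.73/0.85 and 0.75/0.91/0.95. The mean estimate was 0.79 points for all three contrasts, and type I error was 0.048 to 0.052 for each contrast fixed in advance.

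**Leaving the choice open.** In null simulations (20,000 runs per r, r = 0.3 to 0.7), raw or change was significant in about 9% of runs, and at least one of the three contrasts in 9 to 10%.

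**The case against.** The strongest reply is that the gain is conditional. A single 9-point item rated five hours apart, after cognitive demand and in a sample restricted on PSS, could have a low r, and then adjustment adds little to the raw 5h contrast. That stands as a limit on size. It does not favour leaving 0h calmness out: the adjusted contrast is never materially worse, and at low r the change contrast, which the plan also allows, is much worse.

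Other points, and what remains of them:
- **The covariate list is open, so 0h calmness could enter.** True. Under an AIC rule it would be kept about 97% of the time at r = 0.3 if it were considered. But the plan neither says it will be considered nor names a fit criterion. The power loss comes from its not being named; the fit rule is a prespecification problem.
- **Other covariates may already explain some 5h variance.** Fair. The figures compare with a model without covariates, so the extra gain could be smaller. The documents do not allow this to be sized.
- **ANCOVA conflicts with keeping subjects who have missing data.** This is right for standard ANCOVA, which drops anyone lacking either rating. The mixed model with a common 0h mean does not have this problem.
- **The fall from 81% to 76% comes from how attrition was handled.** Agreed; that is a separate matter and is not attributed to this omission.
- **The homogeneity statement is incidental.** Also agreed: it is a wording error on which no figure here depends.

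**Conclusion.** The concern holds. The plan measures 0h calmness, gives it no analytic role and names no primary model term, so it can yield a less precise contrast than the data support. With 117 evaluable, d = 0.5 on a single rating and equal SDs, the gain over the better simple contrast is about 4, 11 and 3 percentage points at r = 0.3, 0.5 and 0.7. The worst gap within that range is 18 points (change 62% against adjusted 80% at r = 0.3). The unknown r and the undefined scale of the effect size change the size of the gain, not its direction: adjusted power was highest in every scenario computed for r of 0.3 or more, and equal to raw at r = 0.

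This is a loss of precision and of prespecification. Each contrast, fixed in advance, is unbiased and holds its 5% error. The 9 to 10% error rate under free choice is a worst case, not a prediction of conduct. The point should be fixed before the data are analysed.

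**What to change.** 1. **Primary Outcome Variable and Analysis:** state that the primary estimate is the lemon balm minus placebo difference in mean 5h calmness, adjusted for 0h calmness, with the adjustment kept whatever the model fit.
2. **Analysis:** name one model. The option that fits the existing missing-data rule is a mixed model with 0h and 5h calmness as responses, unstructured covariance and a 0h mean constrained equal across arms. ANCOVA with 0h calmness as covariate is the alternative; if it is chosen, say how participants missing either rating are handled.
3. **Analysis:** make clear that the post-hoc t-tests do not supply the primary estimate.
4. **Section 5:** remove the claim that screening makes the arms homogeneous.

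The cost is SAP wording and one model term, at most one degree of freedom. No new data and no extra participants are needed.

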## 4. Testing protocol

#### Test visits

- Participants will be asked to follow a low polyphenol diet for 48hours and restrict caffeine and alcohol intake 24 hours prior to test visits.
- At the screening visit participants will have a chance to complete the various cognitive and mood tasks that will be delivered at various timepoints on the test day.
- On arrival of the acute test day, participants will be randomly assigned to treatment: 300mg lemon balm or placebo condition.
- Adverse events and vital signs (bp, HR) will be recorded to estimate tolerance.

- Participants will consume a standardised breakfast (2 croissants and a glass of water) and complete the first block of cognitive and mood tasks between 8am-9am.
- After the baseline (0h), participants will complete the same cognitive and mood tasks at specific timepoints (1h following supplementation, 3h and 5h) and will receive a standardised lunch (cheese sandwich with a packet of crisps).

The screening session should take no longer than 3 hours, and the acute test day should take no longer than 6 hours spread out over an 8-hour window (8am-4pm). Participants may withdraw at any time without giving any reason. In addition, a participant will be withdrawn from the study if they request discontinuation, exhibit a serious adverse event to any component of the test product, the participant significantly violates the exclusion or inclusion criteria, an illness emerges and/or opinion is that withdrawal is appropriate.

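### Does pairing a random subject effect with an unstructured within-subject covariance put the mixed-model results at risk?

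*Combined protocol and SAP*

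**What the plan says.** Section 5 of the combined protocol and SAP, under Analysis, sets one method for every repeated outcome: "all repeated measures data will be analysed using Linear Mixed Modelling (LMM) in RStudio v4.0". It describes the within-subject dependence in two places. The first carries no condition: "Subjects will be included as a random factor as a way of controlling for non-independence of data from the same subjects". The second does: "Where possible, an unstructured covariance matrix will be specified for the repeated observations on a subject within the same period". No model equation is given, no random slope is named, and the text does not say what replaces the unstructured matrix if it cannot be fitted.

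The design is two parallel groups with a single dosing day (section 4, Test visits): "On arrival of the acute test day, participants will be randomly assigned to treatment: 300mg lemon balm or placebo condition". The primary calmness rating has two time points, "measured using a 9-point Likert Scale, at baseline (0h) and 5 hours post administration". The exploratory mood and cognition outcomes have four, "measured at baseline (0h), 1h, 3h and 5h post administration".

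**The concern.** Three things catch the eye.

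- With one test day per participant, an unstructured matrix already carries all the within-subject correlation. A subject intercept on top of it cannot be separately identified, and an over-parameterised fit may fail to converge.
- Only the unstructured matrix is conditional. Read literally, an analyst whose fit fails could drop it and keep the random intercept. That imposes equal variance at every time and equal correlation between every pair of times.
- The mention of a period suits a multi-period design, which this is not.

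At stake is the standard error under that fallback. If correlation decays over the day, a random intercept alone makes the 0h to 5h change look too precise and the 0h to 1h change too imprecise. The second error would cost power at the time when, according to section 1, earlier trials saw effects "beginning with changes first observed after 1h and maintained throughout the test day".

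**Working it through.** **Inputs.** Two time points for calmness and four (0, 1, 3, 5h) for the exploratory outcomes come from the outcome sections. Section 1 gives 130 participants and 10% attrition: 130 × 0.9 = 117 completers, about 58 per arm. The plan states no figure on covariance to reproduce. It gives no SDs or correlations, so those below are assumptions, shown as ranges.

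**Step 1: the redundancy.** The marginal covariance is V = σ_b²J + U, where J is a matrix of ones and U is unstructured. U has T(T+1)/2 free elements: 3 for T = 2 and 10 for T = 4. Adding σ_b² gives 4 and 11 parameters, but V still has only 3 and 10 distinct elements. The rank is therefore 3 of 4 and 10 of 11. Every split with the same sum gives the same V, and so the same likelihood, fixed effects and standard errors.

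**Step 2: fallback, primary outcome.** With complete data, a random-intercept fit estimates the mean variance and the mean covariance. Write v₀ and v₅ for the variances and c for the covariance.

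- *0h to 5h change.* Model variance: 2[(v₀ + v₅)/2 − c] = v₀ + v₅ − 2c, which is the true variance. The standard-error ratio is 1.00 and the type I error 5.0%, whatever the SDs and correlation.
- *5h group contrast read from the model.* Ratio r = √{[(v₀ + v₅)/2]/v₅}; type I error = 2P(Z > 1.96r).

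| SD at 0h → 5h | r | Type I error |
|---|---|---|
| 1.5 → 1.65 (+10%) | 0.956 | 6.1% |
| 1.5 → 1.8 (+20%) | 0.920 | 7.1% |
| 1.5 → 2.0 (+33%) | 0.884 | 8.3% |
| 2.0 → 1.8 (−10%) | 1.057 | 3.8% |
| 2.0 → 1.5 (−25%) | 1.179 | 2.1% |

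For example, 1.5 → 2.0: √[(2.25 + 4)/2 ÷ 4] = √0.781 = 0.884. An independent t-test on the 5h ratings does not use this model variance and is unaffected.

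**Step 3: fallback, exploratory outcomes.** Assume equal variances and correlation = reliability × 0.9^hours. At reliability 1.0 the six pairwise correlations are 0.900, 0.729, 0.590, 0.810, 0.656 and 0.810, with mean 0.749. The ratio is √[(1 − mean correlation)/(1 − correlation of the pair)]:

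- 0h to 5h: √(0.251/0.410) = 0.782
- 0h to 1h: √(0.251/0.100) = 1.583

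Power at 1h, for a contrast with 80% power under the correct model, is P(Z > 1.96r − 2.80).

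| Reliability | 0h–5h r | 0h–5h type I error | 0h–1h r | 0h–1h type I error | 0h–1h power |
|---|---|---|---|---|---|
| 1.0 | 0.782 | 12.5% | 1.583 | 0.2% | 38% |
| 0.8 | 0.871 | 8.8% | 1.196 | 1.9% | 68% |
| 0.5 | 0.942 | 6.5% | 1.066 | 3.7% | 76% |

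Under equal correlations the error is zero. A different assumed pattern, first-order autoregressive by visit with correlation 0.3 to 0.9, gives 7% to 13% for the 0h to 5h change. Simulation with 58 per arm (40,000 runs) agrees: 12.7%, 9.1% and 6.7% for 0h to 5h in the table above, and 5.2% to 5.3% for the two-time change.

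**Step 4: how likely is the fallback?** The unstructured matrix needs 3 parameters (two times) or 10 (four times) from about 117 participants, so sparse data are an unlikely cause of failure. If the surplus parameter causes the failure, removing the random intercept cures it and leaves the marginal model unchanged.

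**The case for a change.** The best argument for a change is that the random intercept alone complies with the text. The SAP does not define when an unstructured matrix counts as infeasible and lists no alternatives. With many outcomes, the structure could differ from one to the next and be chosen after seeing the fits, which sits badly with the SAP's own promise of consistency between analyses. The redundant term could itself provoke the failure that leads to the fallback. The remedy would cost only a sentence.

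The missing detail is real. The step from there to harm is weaker:

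- The SAP expresses a preference for the unstructured matrix. The random-intercept fallback is permitted only by silence.
- The sentence about subjects as a random factor states a purpose, handling non-independence. It can fairly be read with the covariance sentence as a description of one repeated-measures model.
- The SAP's named example for between-group comparisons is the independent t-test, which is unaffected at 5h. Its wording does not exclude contrasts read from the model.
- The largest figures need perfectly reliable mood and cognitive scores. The 80% starting power at 1h is hypothetical, since section 1 does not tie its calculation to that contrast.
- The reference to a period is loose but has no analytic effect: with one test day it covers every repeated observation.

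Nor is the obvious remedy clearly a gain. A random intercept with sandwich standard errors corrects the standard error, but not bias from a wrong covariance when participants with missing data are retained, as this plan intends. An ordered list of structures would be defensible too. The choice is a matter of preference.

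**Conclusion.** The concern is right about the algebra but does not call for a change. One covariance parameter is surplus, and it alters no treatment estimate or standard error once the model fits. The remaining gap, an undefined feasibility condition with no named fallback, is one a competent analyst fills by fitting the unstructured matrix alone.

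Were the random-intercept fallback used, the primary 0h to 5h change test would stay at 5.0% with complete data. A 5h contrast read from the model would run at 2.1% to 8.3% for SD changes between −25% and +33%. In the exploratory models the 0h to 5h change would run at 6.5% to 12.5%, and 80% power at 1h would fall to between 76% and 38%. These ranges rest on assumed SDs and correlations and on the fallback being used. They were worked out for complete data, with 0h kept as a response; if 0h enters the primary model as a covariate, one observation per participant remains and the issue disappears. Tidier wording would do no harm, but the plan's conclusions do not depend on it.

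### Bonferroni is valid for the post-hoc tests, but Holm's step-down gives the same familywise control and is never less powerful; the gain is modest and limited to exploratory outcomes with several real effects

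*Combined protocol and SAP*

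**What the plan says.** The last sentence of the Analysis section specifies "Post-hoc Bonferroni-corrected parametric tests", with independent t-tests as the example, to estimate how the two arms differ. It then extends the same correction to a second kind of comparison: "or within-group differences between time points, where appropriate". It does not say how many tests form a family or whether families are set per outcome, and it gives no reason for choosing Bonferroni.

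Under Exploratory Outcome Variables, mood and cognition are "measured at baseline (0h), 1h, 3h and 5h post administration". Each such outcome therefore has three post-dose between-arm contrasts and, within each arm, six pairs of time points (4 × 3 / 2).

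The primary outcome, calmness, is assessed "at baseline (0h) and 5 hours post administration", so it has one post-dose between-arm contrast.

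**The concern.** Bonferroni holds every test in a family of m at 0.05/m, whatever happens to the other tests. Holm starts at the same threshold for the smallest p-value and then relaxes it to 0.05/(m − 1), and so on up to 0.05, for as long as rejections continue. It needs no assumption that Bonferroni does not need. Where a treatment effect is present at more than one time, Bonferroni therefore gives up power that Holm would keep at the same familywise level.

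What is at stake is the chance of showing at which times an exploratory outcome differs between arms. Neither the validity of the plan nor its primary conclusion is at risk.

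**Working it through.** **The plan's own figure.** Section 1 gives 65 per group "to achieve a power level of 0.80 at a significance level of 0.05" with effect size 0.5. Reading 0.5 as a standardised difference and the test as two-sided (sidedness is not stated), a two-sample t-test needs 64 per group, 128 in total. With 65 per group its power is 0.808. The stated 130 is therefore matched only before any allowance for attrition (128/0.9 = 142.2, so 143). That mismatch is a separate matter. Here it only means that power should be shown both at 65 per arm and after 10% loss. The plan gives no figure for the post-hoc tests.

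**Inputs.**
- From the documents: d = 0.5; 65 per arm, or 65 × 0.9 = 58.5 after attrition; alpha 0.05; three post-dose times.
- Assumed: two-sided tests; a family of m = 3 between-arm contrasts per outcome; equal correlation r between contrasts. The Analysis section recognises the dependence ("Subjects will be included as a random factor as a way of controlling for non-independence of data from the same subjects") but gives no value, so r was varied from 0 to 0.9.

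**Thresholds for m = 3.** Bonferroni: 0.05/3 = 0.0167 for every test. Holm: 0.05/3 = 0.0167, then 0.05/2 = 0.025, then 0.05, applied to the ordered p-values. Holm's first step is the Bonferroni test and its later thresholds are larger, so no Bonferroni rejection can be lost.

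**Closed-form check of the Bonferroni power.**
- Noncentrality: 0.5 × √(65/2) = 2.85. The two-sided critical value at 0.0167 is 2.394. Power per contrast = Φ(2.85 − 2.394) = Φ(0.456) = 0.68.
- After attrition: 0.5 × √(58.5/2) = 2.704, and Φ(2.704 − 2.394) = Φ(0.310) = 0.62.

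**Simulation** (200,000 draws of equicorrelated normal test statistics, m = 3, r = 0.5). Power is averaged over the truly non-null contrasts:

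| Real effects (d = 0.5) | Per arm | Bonferroni | Holm |
|---|---|---|---|
| three | 65 | 0.677 | 0.753 |
| three | 58.5 | 0.622 | 0.700 |
| two of three | 65 | 0.676 | 0.708 |
| one of three | 65 | 0.675 | 0.676 |

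With all three real, the chance of rejecting all three goes from 0.440 to 0.613 at 65 per arm. The chance of at least one rejection is 0.885 under both methods.

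**Sensitivity to correlation** (three real effects, 65 per arm):

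| r | Average power, Bonferroni | Average power, Holm | Error with all nulls true, both methods |
|---|---|---|---|
| 0 | 0.677 | 0.769 | 0.050 |
| 0.5 | 0.677 | 0.753 | 0.044 |
| 0.9 | 0.676 | 0.732 | 0.030 |

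**Sensitivity to effect size** (three real effects, r = 0.5, 65 per arm): d = 0.3 gives 0.247 to 0.290; d = 0.2 gives 0.106 to 0.123.

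**Sensitivity to the family.** If the baseline contrast were counted as a fourth, null member (r = 0.5, d = 0.5 at the other three), average power goes from 0.639 to 0.689. With m = 1 the two methods are identical.

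**Error control.** In every scenario familywise error was at most 0.05 under both methods. With some nulls false, Holm's error rate was at most 0.044.

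**The case against.** The strongest reply is that Bonferroni is valid and simple, and that these tests are meant to estimate differences. Bonferroni supplies simultaneous intervals that match its decisions, and Holm does not. Choosing between two valid corrections on exploratory outcomes may look like preference. This stands in part. It sets the priority low and obliges the sponsor to say which intervals accompany Holm p-values. It does not alter the fact that Holm is at least as powerful at the same familywise level.

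Nor is the extra power entirely free. With two real effects and one null (r = 0.5), the null is falsely rejected with probability 0.016 under Bonferroni and 0.035 under Holm. Both are inside 0.05, but Holm uses slack that Bonferroni leaves unspent.

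Four stronger readings are tempting, and the documents do not support them:

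- A reader might infer that correlation between time points is what makes Bonferroni the wrong choice. Holm does not use the correlation. With all nulls true its error rate equals Bonferroni's at every r, and its gain shrinks as r rises.
- A reader might infer from Section 1 that the plan expects an effect at all three times, and so take 0.44 to 0.61 for detecting all three as the likely gain. Section 1 reports change from baseline in similar trials. It does not state an expected between-arm difference of 0.5 at each time for each exploratory outcome. The all-three case is the most favourable one.
- A reader might infer that the primary analysis loses power. It has one post-dose between-arm contrast, so the methods coincide.
- A reader might infer that changing one word is enough. Without stated families neither method can be applied unambiguously, and the same sentence also covers within-group comparisons.

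**Conclusion.** The point holds as an efficiency improvement and not as an error. For exploratory outcomes with three post-dose between-arm contrasts, replacing Bonferroni with Holm raises average power per truly non-null contrast from 0.68 to 0.75 if all three effects are real, and to 0.71 if two are. If only one is real there is practically no gain. After 10% attrition the all-real case is 0.62 to 0.70.

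These sizes rest on d = 0.5, two-sided 0.05, a family of three and r = 0.5. Over r from 0 to 0.9 the all-real Holm figure runs from 0.77 down to 0.73, against about 0.68 for Bonferroni throughout. Smaller effects give smaller absolute gains. That Holm never loses a Bonferroni rejection and keeps familywise error within 0.05 depends on none of these assumptions.

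**What to change.** In the last sentence of the Analysis section, replace Bonferroni-corrected with Holm-corrected and add the families, for example:

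*Holm's correction will be applied within each exploratory outcome to the between-arm contrasts at 1h, 3h and 5h (one family of three). Within-group comparisons between time points, if performed, will form a separate Holm family. Confidence intervals will be unadjusted (or Bonferroni-adjusted), will be labelled as such, and may not agree with the Holm decisions.*

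The family definition is needed even if Bonferroni is kept, because the number of tests is not stated at present. The change leaves the planned tests themselves as they are.

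The cost is a few lines in the SAP and one software option, with no change to data, visits or sample size. The one real drawback is the lack of simple simultaneous intervals that match Holm, which the labelling makes explicit. If matching intervals matter more to the sponsor than the extra power, keeping Bonferroni with the family stated is defensible.

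### The independent t-test is the only post-hoc test named, and it is applied to within-person changes over time, where its standard error is too large; the follow-up comparisons should be contrasts from the planned mixed model

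*Combined protocol and SAP*

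**What the plan says.** The Analysis section of the SAP makes the LMM the main method: "all repeated measures data will be analysed using Linear Mixed Modelling (LMM) in RStudio v4.0". It gives the reason for the random subject term: "Subjects will be included as a random factor as a way of controlling for non-independence of data from the same subjects". Where possible, "an unstructured covariance matrix will be specified for the repeated observations on a subject", and "subjects with missing data points will not be excluded from the analyses".

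The section closes with the follow-up comparisons. Bonferroni-corrected parametric tests "such as independent t-tests will be performed to estimate between-group differences between placebo and intervention groups, or within-group differences" are planned, and the sentence ends "within-group differences between time points, where appropriate". No paired test, model contrast or estimated marginal mean is mentioned anywhere in the document, and the set of comparisons that the Bonferroni correction covers is not defined.

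The Primary Outcome Variable section measures calmness "at baseline (0h) and 5 hours post administration". The mood and cognition outcomes, which are exploratory, are "measured at baseline (0h), 1h, 3h and 5h post administration".

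**The concern.** A within-group difference between time points compares the same people with themselves. An independent t-test treats the two sets of ratings as coming from different people and leaves out their covariance. The section introduces a random subject term to deal with exactly this dependence, and then offers as its one example a test that assumes the dependence away.

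Between groups the issue is different. A two-sample t-test at 5h is a valid comparison of randomised arms. As a separate test, however, it uses neither the model's covariates and covariance structure nor its handling of incomplete participants, and it ignores the 0h calmness rating that every participant is due to give.

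At stake are the precision of the reported within-group changes, a gain in power for the primary comparison that needs no new data, and clarity about which number will be reported as the treatment effect. No sentence in the SAP names an LMM term or contrast as the primary test.

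**Working it through.** **Inputs.** Effect size 0.5 (taken as a standardised mean difference), 65 per group, 10% attrition, power 0.80 and significance level 0.05, all from the Sample Size Calculation. A two-sided test is assumed. Completers per arm: 65 × 0.9 = 58.5, taken as 58. The 0h–5h correlation ρ is not in the documents, so 0.3, 0.5 and 0.7 are assumed. SDs at the two times are taken as equal and set to 1.

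**The plan's own figure.** A two-sided two-sample t-test with d = 0.5 needs 64 per arm (128 in all) for power 0.80, and 65 per arm give 0.808. So 130 matches the calculation before attrition. With 58 completers per arm the power is 0.76. That shortfall is a separate sample-size matter; here 0.76 serves only as the starting point for the between-group comparison.

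**Within-group change, n = 58.**
- SE used by the independent test: √(2/n) = √(2/58) = 0.186, whatever ρ is.
- Correct SE (paired or model-based): √(2(1−ρ)/n), for example √(2 × 0.5/58) = 0.131 at ρ = 0.5.
- Ratio: 1/√(1−ρ). It does not depend on n.
- Actual type I error of the independent test at nominal 0.05, before Bonferroni: approximately P(|Z| > t/√(1−ρ)), with t = 1.98 on 114 degrees of freedom.
- Power for a change of 0.3 SD: by simulation (60,000 arms of 58, bivariate Normal).

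| ρ | Correct SE | SE ratio | Type I error: formula (simulated) | Power, independent | Power, paired |
|---|---|---|---|---|---|
| 0.3 | 0.155 | 1.20 | 0.018 (0.019) | 0.34 | 0.48 |
| 0.5 | 0.131 | 1.41 | 0.005 (0.006) | 0.31 | 0.61 |
| 0.7 | 0.102 | 1.83 | 0.0003 (0.0008) | 0.27 | 0.83 |

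The error runs in one direction for positive ρ: intervals are too wide and true changes are missed.

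**Between-group difference at 5h, d = 0.5, 58 per arm.**
- Unadjusted: noncentrality 0.5/√(2/58) = 2.69, power 0.76.
- Adjusted for the 0h rating: the SE is multiplied by √(1−ρ²), so the noncentrality is 2.69/√(1−ρ²), with one degree of freedom fewer.

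| ρ | SE multiplier | Noncentrality | Power |
|---|---|---|---|
| 0.3 | 0.954 | 2.82 | 0.80 |
| 0.5 | 0.866 | 3.11 | 0.87 |
| 0.7 | 0.714 | 3.77 | 0.96 |

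**The case against.** The strongest reply is that the sentence is illustrative. It introduces the t-test with *such as* and ends with *where appropriate*, so a paired test or a model contrast is not excluded and a competent analyst would choose one. That stands as a limit on the claim: the independent t-test is an example, not a fixed rule. It does not remove the problem, because the one example given is unsuitable for half of its stated use, and the plan leaves the real choice open until the data are in hand.

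Four stronger readings are tempting, and the documents do not support them.

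- *The mixed model is abandoned.* It is not. It remains the stated analysis of all repeated measures. Only the follow-up step is not tied to it.
- *All the t-tests have wrong standard errors, or produce false positives.* The between-group standard error at a single time is valid, and the within-group error is conservative when the correlation is positive. The primary question is between groups, so the within-group error does not touch it. Nor does the SAP say that a within-group change will count as evidence of efficacy.
- *The gap from 0.76 to 0.87 is power lost against the model already planned.* The 0h calmness rating is not among the listed covariates. If 0h is simply one of the repeated responses, with separate group means at each time, an unstructured covariance and complete data, the model's 5h contrast is the raw mean difference and has essentially the same precision as the t-test. The gap is what an added baseline adjustment would gain.
- *Bonferroni cuts primary power to about 0.61.* That figure divides 0.05 by three post-dose times. The primary outcome has one post-dose time, 5h; the times 1h, 3h and 5h are listed for the exploratory outcomes. What can fairly be said is that the correction's scope is undefined and the primary contrast is not expressly exempted.

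**Conclusion.** The point holds in limited form. The wording conflicts with the section's own reason for modelling subjects as random, and applied literally it would nearly halve the power to detect a 0.3 SD within-arm change at a correlation of 0.5. The consequence is lost precision in secondary comparisons, with no threat to the validity of the primary one. The larger practical benefit is on the primary outcome, where using the 0h rating would bring power back to about the planned 0.80 even at a correlation of 0.3.

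These sizes rest on assumed correlations, equal SDs at the two times, approximate Normality of a 9-point rating, a two-sided test and 58 completers per arm. The direction of the results needs only a positive correlation between a person's ratings. The change is worth making before the analysis begins, but the trial's main inference would survive without it.

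**What to change.** Replace the closing sentence of the Analysis section with wording such as:

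*All comparisons are contrasts of estimated marginal means from the fitted LMM. The primary test is the between-group contrast in calmness at 5h, adjusted for the 0h rating, at two-sided 0.05 and without Bonferroni correction. Post-hoc contrasts are Bonferroni-corrected within each outcome. Within-group changes are estimated from the same model and reported descriptively; they are not used as evidence of a treatment effect.*

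One detail should be settled at the same time. If 0h enters only as a covariate, the primary calmness analysis has a single response per person and reduces to ANCOVA, and changes from 0h are no longer direct contrasts of that model. Keeping 0h as a response, with one common 0h mean for the two randomised arms, gives both the baseline-adjusted 5h contrast and the within-group changes from one model. It also retains participants who have only one of the two ratings.

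The cost is this SAP wording and a few lines of R code. No new data, visits or participants are needed.
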